## 3) IRB Review History

N/A

## 4) Objectives

In this pilot study, we propose to randomize 20 participants with Alcohol Use Disorder (AUD) to treatment with either placebo or 600 mg of gemfibrozil twice daily for 4 weeks in a **double-blind placebo-controlled, clinical trial**. Participants will receive 4 sessions of motivational enhancement therapy (MET), regardless of medication assignment. Brain responses during response inhibition, stress, and alcohol cue reactivity will be measured with fMRI obtained at baseline and 2 weeks. Triglyceride levels will be obtained at baseline, 2 and 4 weeks. The protocol will be registered on clinicaltrials.gov.

**Aim 1: To investigate the effects of gemfibrozil on alcohol use at 4 weeks in individuals with AUD.** We hypothesize that relative to placebo, gemfibrozil will improve alcohol use outcomes as defined by rate of change in drinks per drinking day (DPDD), drinks per week (DPW) and percent days abstinent (PDA). Effect sizes for all 3 metrics will be calculated to determine if a larger clinical trial is warranted.

**Aim 2: To investigate the effects of gemfibrozil on various possible biological targets which are increasingly recognized as important mechanisms by which treatments for AUD work.** In particular we hypothesize that gemfibrozil will result in 1) increased engagement of cognitive control networks (inferior frontal gyrus (IFG) and dorsal anterior cingulate cortex (ACC)) during response inhibition, 2) decreased response in networks involved in reward (ventral and dorsal striatum, ACC) during the presentation of alcohol cues, 3) decreased response in networks that process negative affect [amygdala, insula, and ventromedial prefrontal cortex (PFC)] in response to emotional pictures, and 4) reduced triglyceride levels. We also hypothesize that changes in these targets will mediate the effects of gemfibrozil on alcohol use at 4 weeks.

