## 5) Background

Alcohol dependence accounts for 4% of the global disease burden, and has significant individual and societal costs. While three FDA approved medications are available for the treatment of AUD, effect sizes tend to be modest, and findings do not replicate from study to study. Identifying additional treatments for AUD is sorely needed in order to improve the number of options available to prescribe to patients with an AUD.

Peroxisome proliferator-activated receptors (PPARs) are nuclear hormone receptors that heterodimerize with the retinoid X receptor, which, in combination, are able to modify the transcription of target genes within the cell nucleus. There are three main classes of PPARs including  $\alpha$ ,  $\beta/\delta$ , and  $\gamma$ , which are distributed throughout the body including the brain. In fact, PPAR  $\alpha$  and  $\delta$  are both expressed highly in regions within reward networks including nucleus accumbens, ventral tegmental area, and amygdala and also in prefrontal cortex, which may suggest a potential effect on executive control. PPAR  $\alpha$  agonists show potential for beneficial effects on depression, neuro-degeneration, learning and memory deficits following ischemia, pain epilepsy

obesity and inhibition/cognitive control. Fibrate medications (fenofibrate, gemfibrozil), which are derivatives of fibric acid, are a class of medications commonly used in the treatment of hypercholesterolemia (especially hyperlipidemia Type III, due to its effect of lowering very low density lipoprotein) and are widely used to reduce peripheral levels of triglycerides. Fibrates are also agonists at the PPAR  $\alpha$  receptor.

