#### Intervention

Participants who meet study criteria will be randomized to active treatment or placebo. The placebo group will receive capsules (filled with microcrystalline cellulose powder) which look identical to capsules filled with active treatment, and will receive the same number of capsules as for active treatment. Members of the study team will be blinded to study randomization; the study pharmacist and/or another honest broker at MRN (e.g. member of the Research Operations team) will be un-blinded, and the pharmacist will not interact with any of the participants. Gemfibrozil will be prescribed at 600 mg by mouth twice daily, *which is the standard FDA approved dose used for the treatment of hypertriglyceridemia*. Adherence will be monitored with bi-weekly pill counts. At the first med dispensing visit (30 minutes, baseline), participants will receive basic information about possible side effects and will be provided with a 2-week supply. During the follow-up med dispensing visit at Visit 5 (15 minutes), individuals will undergo a review of side effects.

All individuals will also receive 4 sessions of motivational enhancement therapy (MET), thus reducing ethical concerns of non-treatment. Therapists will be trained by a MINT-trained trainer.

#### Visit 4

One week after starting medication, participants will complete the second MET session. In addition, participants will complete TLFB, PACS, Helping Alliance Questionnaire, and the CIWA. Expected time: 30 minutes

### Visit 5

Two weeks after starting medication, an additional two weeks of medication will be dispensed, the third MET session will take place, and a follow-up MRI scan (identical to baseline scanning session), blood draw, and assessments will take place. The blood draw will be used to measure LFT's, GGT, and triglyceride levels. Assessments will include the CIWA to measure withdrawal, the ICS to measure impaired control, the PACS to measure craving, the TLFB to measure drinking, the Helping Alliance Questionnaire, and medication side effects. Expected time: MET (30 minutes), MRI (1 hour), Med dispense (30 minutes), Assessments/blood draw (1.5 hours)

### Visit 6

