Four weeks after starting medication, the fourth MET session will take place as well as a blood draw and assessments. The blood draw will be used to measure assess LFT's, GGT, and triglyceride levels. Assessments will include the CIWA to measure withdrawal, the ICS to measure impaired control, the PACS to measure craving, the TLFB to measure drinking, the Helping Alliance Questionnaire, and medication side effects. Expected time: MET (30 minutes), Assessments/blood draw (2 hours)

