### Phone Call

Six weeks after starting medication, a phone assessment will be used to collect TLFB and PACS data and side effects/other symptoms that may be associated with terminating use of the medication. Expected time: 30 minutes

For all questionnaires listed above, participants may refuse to answer any question at any time. Direct identifiers will be collected and maintained in the MRN COINS database. All data collected as part of this study will be coded with a Unique Research Subject Identifier (URSI).

Instrument/Activity	Screen (Visit 1)	Screen (Visit 2)	Baseline (Visit 3)	Visit 4	Visit 5	Visit 6	Phone Call
Breathalyze	X		X		X		
SCID	X						
TLFB	X		X	X	X	X	X
MRI Screener	X		X		X		
Edinburgh Handedness	X						
Urine Drug Screen	X		X		X		
Pregnancy Test	X		X		X		
Exclusion Criteria List		X					
Medical History		X					
Physical Exam		X					
Blood draw		X			X	X	
PACS			X	X	X	X	X
ICS			X		X		
CIWA			X	X	X		
ADS			X				

FTND			X				
AUDIT			X				
WTAR			X				
DERS			X				
S-DERS			X				
ERQ			X				
PROMIS Anger			X				
PROMIS Depression			X				
PROMIS Anxiety			X				
MCQ			X				
Emotional WM			X				
Digit Span			X				
DRINC			X				
Helping alliance Questionnaire			X	X	X	X	
SoCRArTES			X				
Treatment Services Review			X				
Demographics			X				
Locator			X				
MRI			X		X		
Motivational Enhancement Therapy			X	X	X	X	
Medication Dispensing			X		X		
Medication Dosing Handout			X				
Medication Count				X	X	X	X
SAFETEE/Adverse events				X	X	X	X
Total time (hours)	2	2	4.5	.75	3.5	2.5	.5
Total Payment	\$20	\$20	\$60	\$10	\$80	\$50	\$10

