## 17) Risks to Subjects

Gemfibrozil: The risks of the medication are greater than minimal risk. There are three main safety concerns of gemfibrozil in adults: self limited transaminitis, gallstones and rhabdomyelisis. Our methods will allow us to explore for any adverse events in these and unexpected areas, and we will be aggressive about checking liver tests and following up concerning symptoms. We are also checking CK levels (for subclinical rhabdomyelisis) at baseline. To our knowledge there have been no clinical reports of the combinations of gemfibrozil and alcohol causing significant problems, and gemfibrozil is not contraindicated in individuals who also drink alcohol, although patients are warned about the risks of alcohol counteracting the triglyceride lowering effects in the package insert. Moderate amounts of alcohol co-administered with gemfibrozil in rats did not cause alterations in LFTs and authors concluded that a moderate amount of alcohol with gemfibrozil is safe in rats. Based on their association with gemfibrozil treatment in past work, stomach upset or pain, diarrhea, nausea, or vomiting will be monitored for using a standard checklist as well as symptoms of more serious side effects (right upper quadrant abdominal pain, nausea, vomiting would be concerning for gallstones; muscle aches or weakness, dark colored urine would be concerning for rhabdomyolisis). The FDA has determined this medication to be exempt from needing an IND (see attached IND exemption letter – gemfibrozilINDExempt.pdf).

MRI: Radio and magnetic waves associated with MRI scans are not associated with any known adverse effects. MRI is non-invasive and considered minimal risk by the FDA and OHRP. However, the scanner is a large magnet, so it could move objects containing ferrous metal in the room during the scan. All participants are screened using the MRI safety screening form prior to being scanned. Participants may be bothered by feelings of claustrophobia (uncommon). The MRI also makes loud ‘drum’ beating noises during the study. Headphones or earplugs are

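### Does Aim 2 need to fix which triglyceride change is the mediator, and which drinking days it should explain?

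*Combined protocol and SAP*

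**What the plan says.** Section 4 (Objectives) lists four Aim 2 targets: three brain responses and triglycerides. It then adds the mediation hypothesis: "We also hypothesize that changes in these targets will mediate the effects of gemfibrozil on alcohol use at 4 weeks". The measurement times are given just before the aims: brain responses are "measured with fMRI obtained at baseline and 2 weeks. Triglyceride levels will be obtained at baseline, 2 and 4 weeks". The drinking outcome comes from Aim 1: "gemfibrozil will improve alcohol use outcomes as defined by rate of change" in drinks per drinking day, drinks per week and percent days abstinent, at 4 weeks.

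The visit descriptions in Section 10 agree with this. At Visit 5 (week 2), "a follow-up MRI scan (identical to baseline scanning session), blood draw, and assessments will take place". At Visit 6, "Four weeks after starting medication, the fourth MET session will take place as well as a blood draw and assessments"; the TLFB is among those assessments. Later, "Six weeks after starting medication, a phone assessment will be used to collect TLFB and PACS data".

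The only analysis text is the Statistical Analysis paragraph of Section 13. It names linear mixed models and the general linear model, says that power will probably be insufficient, and promises effect sizes. It gives no mediation model, mediator time point, outcome window or significance level.

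**The concern.** A mediator should come before the outcome that it is meant to explain. A week-4 triglyceride value is drawn on the day the 4-week drinking record closes, so it comes after all of that drinking.

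The reverse path is plausible on the protocol's own account. Section 17 reports that "patients are warned about the risks of alcohol counteracting the triglyceride lowering effects in the package insert". If drinking in weeks 3-4 raises triglycerides, participants who drink less will show lower week-4 triglycerides whatever the mechanism. That artefact points in the hypothesised direction. A test that requires both paths would give limited protection, because the first path is expected to be strong: Section 5 describes fibrates as "widely used to reduce peripheral levels of triglycerides".

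With two change scores and an open outcome window, an analyst could also choose after seeing the data. At stake is the credibility of one mechanistic result, that for triglycerides.

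**Working it through.** The plan gives no figure to reproduce. The check has two parts.

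**1. Time order.** Take the draws at days 14 and 28 (nominal).

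| Outcome days | After the week-2 draw | After the week-4 draw |
|---|---|---|
| 1-28 | 14 of 28 | 0 of 28 |
| 15-28 | 14 of 14 | 0 of 14 |
| 29-42 (phone call) | 14 of 14 | 14 of 14 |

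The last row is not drinking at 4 weeks. A week-4 mediator therefore has no outcome days after it, and a week-2 mediator has half, unless the window starts after Visit 5.

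**2. Size of the artefact.** From the plan: 20 randomized, and 70-80% expected to complete at least two weeks (Section 9), so n = 14 to 20. Everything else is assumed:

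- There is no true mediation.
- Weekly changes in drinking from baseline, W1 to W4, are exchangeable. Half-period means H1 (weeks 1-2) and H2 (weeks 3-4) have SD 1 and correlation 0.6. This implies weekly covariance 0.6 and weekly variance 1.4, because (1.4 + 0.6)/2 = 1.
- The triglyceride change has within-arm correlation r = 0.3 or 0.5 with drinking in the preceding two weeks: H1 for the week-2 draw, H2 for the week-4 draw.

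With arm in the model, the spurious partial correlation is r × corr(driver, outcome).

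*Slope from baseline to week 4.* The slope is proportional to −W1 + W3 + 2·W4.
- Variance: 1.4 × 6 + 2 × 0.6 × (−1 − 2 + 2) = 7.2, so SD = 2.683.
- Covariance with H1: (0.4 + 1.2)/2 = 0.8, so the correlation is 0.8/2.683 = 0.298.
- Covariance with H2: (2.0 + 2.8)/2 = 2.4, so the correlation is 2.4/2.683 = 0.894.
- Spurious correlation: week 2, 0.09 or 0.15; week 4, 0.27 or 0.45.
- If all four weeks drive the week-4 value, corr = 1.6/(0.894 × 2.683) = 0.667, giving 0.20 or 0.33.

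*Mean change over weeks 1-4.* Variance (1 + 1 + 1.2)/4 = 0.8; covariance with either half (1 + 0.6)/2 = 0.8; correlation 0.8/√0.8 = 0.894. Week 2 and week 4 both give 0.27 or 0.45.

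*Slope over weeks 1-4 only.* Weights −3, −1, 1, 3; variance 0.8 × 20 = 16; covariance with H1 is 0.8 × (−2) = −1.6 and with H2 is +1.6. The correlations are −0.4 and +0.4: equal in size, opposite in sign. If all four weeks drive the week-4 value, its correlation is 0.

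*Mean of weeks 3-4, unadjusted.* The week-2 draw precedes every outcome day, yet corr(H1, H2) = 0.6 still leaves 0.18 or 0.30.

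The Fisher approximation for a two-sided 5% test is P(|Z + atanh(ρ)·√(n − 4)| > 1.96). Example: ρ = 0.268, n = 20 gives 0.275 × 4 = 1.10, hence 19.6%. Simulation (20,000 trials per cell) gave about 20%. False-positive rates of the triglyceride-drinking path, n = 14 to 20:

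| Outcome | Mediator | r = 0.3 | r = 0.5 |
|---|---|---|---|
| Slope, baseline to week 4 | week 2 | 6-7% | 7-9% |
| | week 4, weeks 3-4 driver | 14-20% | 34-51% |
| | week 4, all-weeks driver | 10-13% | 20-30% |
| Mean change, weeks 1-4 | week 2 | 14-20% | 35-51% |
| | week 4, weeks 3-4 driver | 14-20% | 34-51% |
| Slope, weeks 1-4 | week 2 (negative sign) | 7-8% | 10-13% |
| | week 4, weeks 3-4 driver (positive sign) | 7-8% | 10-13% |
| Mean of weeks 3-4 (Fisher only) | week 2 | 9-11% | 17-24% |

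Requiring both paths to be significant in the hypothesised direction, with an assumed 1 SD drug effect on triglycerides and a slope from baseline, gives 2-4% or 4-6% for week 2 and 7-13% or 18-37% for week 4 (weeks 3-4 driver). With mean change over weeks 1-4, week 2 also reaches about 7-13% or 18-37%.

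*Precision.* A null partial correlation has a 95% interval of ±tanh(1.96/√16) = ±0.45 at n = 20 and ±tanh(1.96/√10) = ±0.55 at n = 14.

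**The case for a change.** The best argument for a change is that it costs a few sentences and no data: name the week-2 change as mediator, name the TLFB days, and call the analysis exploratory. Mediation is a stated hypothesis, low power does not correct a directional bias, and an undeclared choice invites selection. The plan says rate of change, so a slope from baseline is the most literal outcome, and for it week 2 is clearly better.

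Much of this stands. The time point and the days are unstated, a week-4 mediator would be a poor choice, and a good analysis report would say which values were used. Three things weaken the case for amending the plan.

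- The preference for week 2 holds for one reading of the outcome. It disappears for a mean change, and for a slope within weeks 1-4 only the sign of the bias differs.
- The change would not secure the time order it is meant to secure. Half of the 4-week outcome days still precede the week-2 draw. Moving the outcome to drinking after Visit 5 restores the order, but it leaves the Aim 1 outcome, still carries spurious correlation, and if adjusted for early drinking removes true mediation that acts through early drinking.
- The error rates presuppose a 5% test that the plan does not set, and correlations that no document supplies. Section 17 relays a package-insert warning, which supports plausibility but not a size.

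**Conclusion.** This is a small gap in specification that analysts can fill sensibly, and the harmful version is not in the plan. Nothing directs anyone to the week-4 change. The other three mediators exist only as changes to week 2, so using the same interval for triglycerides is the obvious choice. The week-4 value keeps a clear use in describing the drug's effect on triglycerides, itself an Aim 2 hypothesis. Both aims refer to 4 weeks, and the later phone call falls after treatment, so there is little real doubt about weeks 5-6.

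With that default and a slope from baseline to week 4, the false-positive rate is about 6-9% instead of 5%. With other outcome definitions it could reach 51%, but there a week-4 mediator does no better, unless all four weeks drive it and the slope covers weeks 1-4 only (nominal 5%). These figures rest on r of 0.3 to 0.5, a between-half drinking correlation of 0.6 and n of 14 to 20; only n comes from the plan.

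The consequence is limited to one of four mediators in a 20-person pilot that expects too little power and offers effect sizes. An interval of about ±0.45 to ±0.55 would not support a firm mechanistic claim from either draw. The Aim 1 effect sizes, on which the case for a larger trial rests, do not use the mediator. No change to the plan is called for.

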## 5) Background

Alcohol dependence accounts for 4% of the global disease burden, and has significant individual and societal costs. While three FDA approved medications are available for the treatment of AUD, effect sizes tend to be modest, and findings do not replicate from study to study. Identifying additional treatments for AUD is sorely needed in order to improve the number of options available to prescribe to patients with an AUD.

Peroxisome proliferator-activated receptors (PPARs) are nuclear hormone receptors that heterodimerize with the retinoid X receptor, which, in combination, are able to modify the transcription of target genes within the cell nucleus. There are three main classes of PPARs including  $\alpha$ ,  $\beta/\delta$ , and  $\gamma$ , which are distributed throughout the body including the brain. In fact, PPAR  $\alpha$  and  $\delta$  are both expressed highly in regions within reward networks including nucleus accumbens, ventral tegmental area, and amygdala and also in prefrontal cortex, which may suggest a potential effect on executive control. PPAR  $\alpha$  agonists show potential for beneficial effects on depression, neuro-degeneration, learning and memory deficits following ischemia, pain epilepsy

obesity and inhibition/cognitive control. Fibrate medications (fenofibrate, gemfibrozil), which are derivatives of fibric acid, are a class of medications commonly used in the treatment of hypercholesterolemia (especially hyperlipidemia Type III, due to its effect of lowering very low density lipoprotein) and are widely used to reduce peripheral levels of triglycerides. Fibrates are also agonists at the PPAR  $\alpha$  receptor.

Not surprisingly, these medications are now being explored for the treatment of addictive disorders, and particularly AUD. There have been some promising results from preclinical trials suggesting that PPAR  $\alpha$  agonists may reduce drinking. Blednov et al found that fenofibrate administration reduced ethanol consumption in both continuous and intermittent 2-bottle choice tests in male mice, although no effect was found for females. In addition, fenofibrate and tesaglitazar administration reduced novelty responses and increased acute withdrawal, and fenofibrate increased conditioned taste aversion, all of which could explain reductions in drinking. In a separate set of studies, administration of pioglitazone, a PPAR  $\gamma$  agonist, reduced drinking and alcohol seeking in rats. Also, inadvertent reductions in alcohol consumption have been observed in trials of gemfibrozil for triglyceride reduction in humans. A phase 2 clinical trial of fenofibrate administered over 9 days in non-treatment seeking individuals with at least a moderate AUD was recently completed, looking at effects of fenofibrate on cue induced craving and drinking (clinicaltrials.gov/ct2/show/NCT02158273). However, based on results posted on clinicaltrials.gov, findings were not robust. However, no clinical trials to date have focused on testing the effect of gemfibrozil on drinking related outcomes in human subjects with AUDs.

Gemfibrozil may have some advantages over fenofibrate, and thus warrants further study. For one, although fenofibrate is more widely used due to its greater efficacy in reducing triglycerides, smaller effects on the CYP450 system, and lower risk for rhabomyelitis, gemfibrozil may have less liver toxicity, and both medications are equally safe. Moreover, although fenofibrate showed some promise in animal models for nicotine use reduction, it did not reduce smoking in humans and only modestly reduced smoking withdrawal. Importantly, fenofibrate may have limited ability to cross the blood brain barrier, whereas preclinical studies have shown that gemfibrozil definitively increases binding to PPAR receptors in the brain. Gemfibrozil reaches peak plasma concentrations in humans in one to two hours post-administration and in rats, effects on gene expression are detectable in cortex within three days of use suggesting a relatively fast-acting agent.

*Potential targets of gemfibrozil.* While the precise mechanisms of action in the brain have not been identified with PPAR  $\alpha$  agonists, some preliminary evidence points to mechanisms that may be particularly important for AUDs, which may affect circuits involved in cue reactivity, cognitive control, and/or negative affect. *Behavioral and cognitive control:* PPAR  $\alpha$  agonist treatment in mice improves cognitive flexibility and inhibition in a pharmacological model of ketamine-induced behavioral disinhibition and repetitive behavior in mice genetically predisposed to have repetitive behavior. *Stress reactivity:* PPAR $\alpha$  agonists have also been found to be associated with reduction in depressive behaviors in mice induced by lipopolysaccharide and in normal C57BL/6J mice. *Alcohol Cue Reactivity:* Leptin transport across the blood brain barrier appears to be targeted by gemfibrozil. Prior studies have demonstrated elevated levels of leptin in individuals with an AUD, and that these levels drop significantly after 1-2 weeks of abstinence from alcohol. Given the role of leptin in signaling satiety, increasing leptin transport could reduce craving and urges to drink. In addition to the effects on leptin transport, administration of gemfibrozil and other PPAR  $\alpha$  agonists may affect function of neural networks involved in motivation and reward that are highly relevant to AUDs. Administration of PPAR  $\alpha$  agonists influences gene expression in the amygdala, with a focus on GABAergic interneurons. Activation of PPAR  $\alpha$  receptors is associated with reduced firing of dopamine cells in the VTA as a result of altered activity of nicotinic acetylcholine receptors.

*Triglycerides:* The mechanisms by which fibrates reduce triglycerides is not fully understood; however, possible candidate mechanisms include via its effect on PPAR  $\alpha$  in the liver, which regulates gene expression of enzymes involved in fatty acid oxidation, through changes in hepatic apolipoprotein CIII expression, through inhibition of triglyceride synthesis in the liver, by enhancing clearance of triglycerides, and potentially even through effects on dietary choice.

